11.2. Missing data

Certain crucial variables are needed to accept a CRF as a useful one.

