3.2. Study objectives

MAIN OBJETIVE

The main objective of this project will be

- To determine Epidemiologic and Age Related Characteristics of Geriatric Patients presenting to the ED across Europe.

SECONDARY OBJETIVES

- To evaluate Early Warning Scoring systems (REMS, MEWS and VIEWS Scores) and determine most suitable Geriatric Emergency Medicine Risk Score regarding hospitalization, ICU admission and in-hospital mortality for patients
- To determine the most effective triage elements that can be used to predict hospitalization of geriatric patients presented to ED

- To determine the in hospital mortality and short term mortality rates of the patients above 65 years of age presenting to the ED across Europe.
- Sub analysis of ED discharged patients versus admitted patients for characteristics, comparison to recommended care and re-ED visit.
- Comparison of European data characteristics, investigation, treatment and outcome to similar data in other part of the world.

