5.6. Sample size

- ✓ All of the patients over 65 years who had presented to emergency services due to acute medical or surgical reasons during the 7 days study period are to be included. Patients younger than 65 years of age will be excluded from the study. The patients who had been brought to emergency services after having undergone cardio pulmonary resuscitation by the emergency medical team will be also excluded from the study.
- ✓ We strive for at least 25 patients per site per study period with a complete case report form (CRF). (This number is based on our pilot study, TEDGeS - Turkish Emergency Departments Geriatric Scoring Study)
- ✓ Each participating center will have to enroll all consecutive cases.

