10.4.2. Data quality control

Specific indicators are establishing to evaluated quality of the information basically % of missing data for each variable and % on NA data on each variable.

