10.7. Author Ship

The EGERS Steering committee will be in charge of the coordination of all the articles that will be published.

The 1st author will be the one that writes the article

3 positions as authors will be dedicated to members of the EGERS Steering Committee

Position as author will also be dedicated to people who actually participated in the development of the protocol and in the drafting of the results and also the number of patients with a complete CRF.

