11.3.1. Sample size

As this is a descriptive study, a formal sample size calculation has not been performed.

Based on our past experience of similar studies, we would expect to enroll between 40 and 50 sites each with an average number of patients of at least 25/site per 7 days study period.

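### Section 11.2 accepts or refuses the whole CRF on unnamed crucial variables, which can undo consecutive sampling and leaves the resulting selection unreported

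*Combined protocol and SAP*

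**What the plan says.** The whole of Section 11.2 (Missing data) is one sentence: "Certain crucial variables are needed to accept a CRF as a useful one". It does not list the variables, say what a CRF must be useful for, or say what happens to a CRF that is not accepted. Section 11.1 (Data Analysis) adds no rule on denominators, imputation or sensitivity analysis.

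The surrounding text bears on this in four places:

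- Section 3.2 gives the main objective as "To determine Epidemiologic and Age Related Characteristics of Geriatric Patients presenting to the ED across Europe".
- Section 5.6 says "Each participating center will have to enroll all consecutive cases", yet it expresses the target of 25 patients per site in complete CRFs. Section 10.7 counts, among the grounds for authorship, "also the number of patients with a complete CRF".
- Section 10.4.2 sets quality indicators, namely the percentage "of missing data for each variable and % on NA data on each variable".
- Section 11.3.1 states that "a formal sample size calculation has not been performed" and expects "between 40 and 50 sites each with an average number of patients of at least 25/site per 7 days study period".

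**The concern.** The rule acts on the record, not on the variable or the analysis. If a non-accepted CRF is not used, a patient with known age, complaint, comorbidities and disposition drops out of all those tables because some other item is blank.

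Consecutive enrolment is this registry's main protection against selection, and a filter applied after enrolment can remove it. If refused patients differ from accepted ones, the described case mix, hospitalisation rate and mortality rate shift. More sites or patients would not reduce that shift.

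The plan also gives the reader no way to judge the shift. It requires no count of non-accepted CRFs and no comparison with accepted ones. The site questionnaire in Appendix 2 asks for all ED presentations in the study week, not those aged 65 or older, so it does not supply the eligible denominator.

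**Working it through.** **Inputs from the documents.** Sections 5.6 and 11.3.1 give 25 patients per site and 40 to 50 sites, so the planned size is at least 40 × 25 = 1000 to 50 × 25 = 1250. There is no formal sample size, refusal rate or missingness rate to reproduce. All refusal shares below are assumptions.

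**Assumed hospitalisation rate.** I take h = 30% of older presenters hospitalised. The 30% in the Section 3.1 pilot results is the elderly share of patients hospitalised from the ED, a different quantity, so it does not support this value.

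**Step 1: effect of unequal refusal on the hospitalisation rate.** Let a and d be the shares of CRFs refused among admitted and discharged patients.

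Observed rate = h(1−a) / [h(1−a) + (1−h)(1−d)]; share lost = h·a + (1−h)·d.

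| a | d | Observed rate | Share lost |
|---|---|---|---|
| 5% | 20% | 0.285/0.845 = 33.7% | 15.5% |
| 5% | 40% | 0.285/0.705 = 40.4% | 29.5% |
| 20% | 5% | 0.240/0.905 = 26.5% | 9.5% |
| 40% | 5% | 0.180/0.845 = 21.3% | 15.5% |
| a = d | a = d | 30.0%, no bias | any |

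**Step 2: a milder model for any characteristic.** Let m be the share of CRFs refused (assumed 5-30%) and RR the ratio of the characteristic's rate in refused to accepted patients (assumed 0.5-2). For a true rate p, the rate among accepted patients is p / [(1−m) + m·RR].

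- p = 30%, m = 30%: RR = 2 gives 0.30/1.30 = 23.1% (−6.9 points). RR = 0.5 gives 0.30/0.85 = 35.3% (+5.3 points).
- p = 6%, m = 30%: RR = 2 gives 0.06/1.30 = 4.62% (−1.38 points). RR = 0.5 gives 0.06/0.85 = 7.06% (+1.06 points). The 6% echoes the pilot's in-hospital mortality and serves only as an example of an uncommon characteristic.
- p = 6%, m = 5%, RR = 2: 5.71% (−0.29 points).
- RR = 1: no bias for any m.

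For comparison, the 95% half-width 1.96·√[p(1−p)/n] at n = 1000 is 2.84 points for p = 30% and 1.47 points for p = 6%. This treats patients as a simple random sample; clustering by site could widen it.

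**Step 3: how large m could be.** If k required items are each independently missing with probability q, the share of CRFs failing is 1 − (1−q)^k. The CRF has eight vital-sign or consciousness entries: systolic and diastolic pressure, temperature, respiratory rate, heart rate, SpO2, additional oxygen and Glasgow Coma Score. The plan does not say these are the crucial variables. If they were, q = 1%, 2% and 5% would fail 7.7%, 14.9% and 33.7% of CRFs.

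**Step 4: effect on numbers.** With m = 5%, 10%, 20% or 30%, 1000 enrolled patients yield 950, 900, 800 or 700 accepted CRFs. For 25 accepted, a site would need 25/(1−m), which rounds up to 27, 28, 32 or 36 enrolled.

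**The case against.** The strongest reply is that Section 11.2 never says a non-accepted CRF is removed from analysis. That is correct: exclusion is an inference. It is nevertheless the natural reading of a rule whose unit is the CRF, and no other section keeps such a patient in any table.

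A reader might go further and infer that the study becomes a complete-case sample. The documents do not support that. The rule covers only certain variables, and Section 10.4.2 expects gaps in individual variables. The complete-CRF wording in Section 5.6 is a recruitment aim, not a definition of the analysis set.

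A reader might also infer that vital signs are the crucial variables and that they go missing for reasons tied to severity. Nothing in the documents says either. If the list were only age, sex and disposition, few records might be lost, and a CRF without age cannot confirm eligibility in any case. Naming the variables could therefore shrink the problem considerably. On its own, though, naming them would still leave refused records unreported.

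Finally, the illustrative figures rest on assumed inputs, and those in Step 1 need a four- to eight-fold difference in refusal between disposition groups. They run in both directions and include zero. This stands, so they show what the rule permits, not what will happen.

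**Conclusion.** The point holds as a risk created by the rule, not as a demonstrated bias. A record-level filter with undefined content conflicts with consecutive sampling and a descriptive main objective, and the plan requires no report from which the resulting selection could be judged.

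A reader might conclude that the main results will be biased, or biased in a known direction. The documents support neither conclusion, because they give no refusal rate and no difference between refused and accepted patients. Over the assumed ranges, the effect on a 30% hospitalisation rate runs from none to an observed 21.3% or 40.4%, with about 10-30% of records lost. Under the milder model it runs from −6.9 to +5.3 points, against a sampling half-width of about 2.8 points at 1000 patients. For a 6% rate it runs from −1.38 to +1.06 points, against about 1.5.

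The effect may thus be nil, negligible or larger than sampling error. The plan should be changed because a better rule costs little.

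**What to change.** Replace Section 11.2 with a rule along these lines:

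- Every enrolled eligible patient, with age confirmed as 65 or older, stays in the descriptive analysis set. Each table row shows n and % missing for its variable.
- Complete score inputs are required only for the ROC analyses. The inputs for REMS, MEWS and VIEWS are listed before data lock.
- The number, site and disposition of patients with incomplete scores or non-accepted CRFs are reported.
- Optionally, a sensitivity analysis multiply imputes missing score inputs.

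Keeping all records removes the whole-record selection; missingness within individual variables remains, but it becomes visible. No new data are needed, provided incomplete CRFs are kept in the database.

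The costs are denominators that differ between table rows and a little more analysis work. If the change counts as a protocol modification, Section 10.3.1 requires steering committee acceptance and local ethics approval, and Section 10.3.2 allows no change during recruitment, so timing matters.

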11.3.1. Sample size

As this is a descriptive study, a formal sample size calculation has not been performed.

Based on our past experience of similar studies, we would expect to enroll between 40 and 50 sites each with an average number of patients of at least 25/site per 7 days study period.

Appendix 1: Case Report Form

EGERS CRF

European Geriatric Emergency Departments Registry Study

Inclusion criteria: All consecutive patients aged 65 or older presenting to the Emergency

Proposed study period, 7 consecutive days from 19th October 2020 to 16th November 2020:
..... (period in which recruitment was performed)

First 3 Letters of the Country |__|__|__| Site |__|__| Patient N |__|__|__|

Day of admission: Monday Tuesday Wednesday Thursday Friday Saturday Sunday

Time of admission: 00:00-08 00 08:01-16 00 16:01-20 00 20:01-23 59

Gender: M F Age (yo) |__|__|__|

Major Presenting Complaint: (Just Check One Major Complaint)

Non-Traumatic Complaint

- Abdominal Pain**
- Agitation and Psychosis**
- The Alcoholic Patient**
- Back Pain**
- Bleeding**
- Chest Pain**
- Dizziness (Vertigo)**
- Extremity Pain and Numbness**
- Fever (Elevated Temperature)**
- Headache**
- Hypotension**
- Jaundice**
- Mental Status Change and Coma**
- Palpitations and Tachycardia**
- Rash**
- Seizure**
- Shortness of Breath**
- Syncope and Near-Syncope**
- Toxic Ingestion**
- Change in Vision**
- Weakness and Fatigue**
- Abnormal findings on examination of blood (Hyperglycemia, Anemia, etc)**
- Other Non trauma.....**
.....
.....

Traumatic Complaint

- Falls**
- Motor Vehicle Accidents**
- Pedestrian Struck**
- Burns**
- Assaults**
- Other Trauma.....**
.....
.....
.....

Presentation Symptoms and Signs:

Systolic Blood Pressure: |_____| mmHg

Temperature: |____|.____| °C

Diastolic Blood Pressure: |_____| mmHg

Respiratory rate/min: |____|

Heart Rate: |_____| bpm

Oxygen saturation (SpO2): |_____| %

Needs additional oxygen supply with nasal cannula or face mask: Yes No

Glasgow Coma Score: Eye:|__| Voice:|__| Motor: |__| **TOTAL: |__|**

Co-morbidities:

 Coronary artery disease	 Dyslipidemia Chronic
 Left Ventricular Failure	 Liver disease
 Right Ventricular Failure	 Chronic inflammatory disease
 Prior coronary revascularization (Bypass)	 Active/recent malignant tumor
 Chronic Obst. Pulm. Disease	 Anemia
 Asthma	 Dementia, Alzheimer
 Chronic renal disease wo routine dialysis	 Immunosuppression/AIDS
 Chronic renal disease with routine dialysis	 Alcohol (> 30g/day for M and > 20 g/day for F)
 Prior stroke (Hemorrhagic or Ischemic)	 Smoking (Active or stopped within last year)
 Diabetes mellitus	 Other.....
 Hypertension

Chronic Medications:

 Beta-blockers	 Oral Antidiabetics
 Calcium antagonists	 Insulin
 ACE Inhibitors or Angiotensin II receptor blockers	 Oral Steroids
 Diuretics	 Cardiac Glycosides
 Statins	 Vit K antagonists
 Antiplatelet	 Psychiatric treatment
 NSAID or Other Analgesics	 Antidepressant
 Inhaled Beta2mimetics	 Antiepileptic
 Inhaled steroids	 Chemotherapy Drugs
 Oxygen +/- NIV at home	 Other.....

Consequence of ED Presentation:	
Final (Hospital or ED for discharged patients) Principal Diagnosis (only one diagnosis):	
 Patient Has Home Care Service  Yes  No  Patient Has History of Falls  Yes  No  Patient Has Temporary Disorientation  Yes  No  Discharged From the Emergency Department Length of stay in ED:         (hours)  Admission to the Emergency Observation unit Length of stay in Obser. Unit:         (hours)  Admitted to Wards  Cardiology  Pneumology  Internal Medicine  Geriatrics  General Surgery  Neurosurgery  Orthopedics/Traumatology  Thorax Surgery  Cardiovascular Surgery  Other  Admitted to Intensive Care Unit  Death at ED  Death during Hospitalization	
For HOSPITALIZED PATIENTS
 
STATUS at 30 days:
 
30 days:  Alive  Death
 
If Admitted to Wards or ICU
 
 Total Length of Stay in Hospital:    (days)
 
 Total Length of Stay in Wards:    (days)
 
 Total Length of Stay in ICU:    (days)
 
 Still in Wards
 
 Still in ICU

Appendix 2

Country questionnaire

Number of ED proposed

Emergency Department Questionnaire

Institution:

Address:

Local PI:

Last name: _____ First name: _____

Phone: _____

e-mail address:

How many patients per year do you receive in your Emergency Department (ED) _____

How many patients per year do you hospitalize either in your hospital or in another hospital: _____

Total number of patients presented to your ED during the study week _____

Population served (habitants) by your ED _____

Is your ED located in a: **(check ONLY ONE BOX)**

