13. OUTCOME VARIABLE

Length of stay in the ED and Length of stay in the hospital if hospitalized.

Status at 30 days: alive or dead.

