5.4. Variables included on the study

Variables are reflected on the Case Report Form

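### ED length of stay is a named outcome with no limit by disposition, but the CRF's only field for it follows the discharge box, with no instruction to complete it for other patients

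*Combined protocol and SAP*

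**What the plan says.** Section 13 names as outcomes "Length of stay in the ED and Length of stay in the hospital if hospitalized", together with 30-day status. Section 14 takes consecutive ED attenders aged 65 or over, whatever happens to them afterwards. Section 5.4 gives no variable list of its own: "Variables are reflected on the Case Report Form".

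On the CRF (Appendix 1, the block on the consequence of the ED presentation), the box "Discharged From the Emergency Department" is followed by a field for ED stay in hours. That field appears once on the form. The next box, for the observation unit, is followed by its own field, "Length of stay in Obser. Unit", also in hours. The boxes for wards, ICU and death in the ED have no ED-stay field. Under "If Admitted to Wards or ICU" the form asks for hospital, ward and ICU stay in days. Arrival is recorded as a weekday and as "Time of admission: 00:00-08 00 08:01-16 00 16:01-20 00 20:01-23 59".

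**The concern.** Section 13 describes an outcome that every attender has, while the form appears to ask for it only from those sent home. If so, the outcome is missing according to disposition and not at random. Any median ED stay would be that of discharged patients, and discharged and admitted patients could not be compared on it, although section 3.2 plans a sub-analysis of those two groups.

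If instead the form leaves the matter open, sites may differ: some would complete the field for admitted patients and others would not. Section 10.4 leaves data quality to local researchers and section 2 lists no study monitors, so the form's own wording is the main safeguard.

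**Working it through.** **1. Scope of the outcome.** Section 13 does not say in terms that ED stay applies to every patient. That follows from two things: the only qualifier in the sentence stands after hospital stay, and the sample is all consecutive attenders. If the qualifier were read as covering both stays, the mismatch would be greater, because the ED-stay field would then sit beside the one group outside the outcome.

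**2. What the form collects for each disposition, as laid out.**

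| Disposition | Stay fields that follow or apply | ED stay recorded? |
|---|---|---|
| Discharged from ED | ED stay (hours) | Yes |
| Observation unit | Observation stay (hours) | Unclear; only if the first field is also used |
| Ward | Hospital, ward stay (days) | No |
| ICU | Hospital, ICU and any ward stay (days) | No |
| Death in ED | None | No |

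**3. Can ED stay be derived from other fields?**

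- *Departure minus arrival.* Arrival is known only to a band: 00:00–08:00 and 08:01–16:00 are 8 hours each, and 16:01–20:00 and 20:01–23:59 are 4 hours each. No time of leaving the ED or of death is asked. The difference cannot be formed.
- *Hospital stay minus ward stay minus ICU stay.* The form does not say whether hospital stay includes time in the ED. Suppose it does, and suppose stays are entered as rounded whole days (both assumptions). Each field then carries an error of up to 0.5 day. With three fields the residual is uncertain by up to 3 × 0.5 = 1.5 days = 36 hours either way; with two fields (ward only) by 2 × 0.5 = 1 day = 24 hours. That is no use for an outcome measured in hours.
- *Death in the ED.* No duration field applies.

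**4. Size.** Section 11.3.1 expects 40 to 50 sites with "an average number of patients of at least 25/site per 7 days study period". The expected minimum is therefore:

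- 40 × 25 = 1,000 patients
- 50 × 25 = 1,250 patients

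Let *p* be the share of patients admitted to a ward or ICU or dying in the ED. Missing values = *p* × N. For each 10 percentage points of *p*:

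- 0.10 × 1,000 = 100
- 0.10 × 1,250 = 125

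Observation-unit patients are left out of *p* because their position is unclear. The documents do not give *p*. The pilot result in section 3.1 that 30% of patients hospitalized from the ED were elderly is the share of admissions who are elderly, not the share of the elderly who are admitted, so it cannot be used for *p*.

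**The case against.** The strongest reply is that the nesting is inferred from layout that has been lost. The relevant part of the form is a table cell collapsed into one run of text, and indentation and line breaks, which would settle the matter, are gone. No skip rule is printed. Where the form wants a restriction elsewhere it prints one, as in "If Admitted to Wards or ICU", and there is none at ED stay. The disposition boxes are not declared mutually exclusive. Data are entered in an electronic system whose logic is not shown. This stands: the documents do not prove that the field is closed to admitted patients. The matching box-and-field pattern for the observation unit makes the nested reading the more likely one, but does not settle it. What survives on either reading is that no instruction says who completes the field, and no other field can stand in for it.

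Section 13 and the form might also be read together as ED stay for those discharged and hospital stay for those admitted. That is possible, but section 13 does not say it, and it would then need rewording.

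The consequence is also limited. No stated objective mentions ED stay, and the ROC analyses in section 11.1 concern hospitalization and in-hospital mortality. This stands and keeps the point below the highest grade.

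Finally, a reader might infer that the quality checks would hide the problem, since section 10.4.2 counts the percentage "of missing data for each variable and % on NA data on each variable" and does not mention disposition. That goes too far. The section presents these as the basic indicators, not a closed list, and disposition is on the same form, so the breakdown needs no new data.

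**Conclusion.** The point holds conditionally. If the form is completed as laid out, a named outcome is missing for every patient admitted to a ward or ICU and every ED death. That means about 100–125 missing values per 10 percentage points of such patients at the expected minimum size, and ED stay could be reported for discharged patients only. This rests on reading the ED-stay field as part of the discharge entry and on the site and patient numbers in section 11.3.1. Confidence is moderate. The change is worth making before recruitment, but the scores, the mortality results and the stated objectives do not depend on it.

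Three stronger readings are tempting and are not supported:

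- *That the loss is established.* Neither the original layout nor the electronic form can be seen.
- *That a total can be given.* Assuming that 20–50% of patients have one of these dispositions would give 0.20 × 1,000 = 200 to 0.50 × 1,250 = 625 missing values, but that range has no source in the documents.
- *That ED stay would be under- or overstated in a known direction.* The documents contain no data on ED stay by disposition.

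**What to change.** Before recruitment starts, make ED stay in hours a stand-alone CRF item, separate from the disposition boxes and marked *complete for every patient, whatever the disposition*. Check the original and electronic forms first: if the field is already open for all dispositions, the instruction alone is enough. Add to the section 10.4.2 indicators a table of missing ED stay by disposition.

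If the field proves to be for discharged patients only and cannot be changed, restate the section 13 outcome as ED length of stay in patients discharged from the ED, and label every summary that way.

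Cost: one extra entry per patient not discharged from the ED, plus steering-committee acceptance and local ethics approval under section 10.3.1. Timing matters, because section 10.3.2 allows no changes once recruitment is under way. The fallback adds no data burden but gives up ED stay for admitted patients and ED deaths, and with it any comparison of discharged and admitted patients on this outcome.
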